## 5. STUDY CONDUCT

### 5.1 Restrictions during the study

1. Male patients must abstain from unprotected sex and sperm donation from the time of dosing until 3 months after the last dose.

Recommended contraception will be double barrier method, ie, male patients must use condoms and, in addition, the female partner should use additional contraception from the time of dosing until 3 months after the last dose. Acceptable methods to be used by female partners include the oral contraceptive pill, hormone implants, intra-uterine devices (IUDs), diaphragms with spermicide.

Male patients should inform the investigator if their partner becomes pregnant during the study.

2. Patients should observe the following restrictions prior to the clinic lung function tests (Visits 1.1, 2 and 3-7):
  - No strenuous exercise within 2 hours
  - No smoking within 1 hour
  - No large meals within 2 hours
3. Use of disallowed concomitant medication (refer to Section 5.6)
4. Patients should not receive a vaccination during the study
5. Patients should abstain from drugs of abuse throughout the entire study
6. Patients should not donate blood at any time during the study and for 12 weeks following completion of the study
7. Patients must not take part in any other study whilst participating in the current study.

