Circulating leucocytes counts (including neutrophils) will be analysed at a local laboratory within 2 hours (maximum 4 hours) of sample draw as circulating neutrophils deteriorate rapidly after blood has been taken. In the main study, on PK days, leucocyte counts will be assessed in blood collected at the same time as AZD5069 concentration. In the PK sub-study, 3 leucocyte samples will be taken at Visit 2 and 2 leucocyte samples will be taken at each of Visits 4 and 6 to match the PK samples taken pre-dose (Visit 2 only), 1 and 3 hours post-dose. The leucocyte results from Visit 2-7 (inclusive) will be blinded from the site staff, refer to Section 5.4.1

Patients taking part in the PK sub-study should take their morning dose of study drug (AZD5069 or placebo) in the clinic after pre-dose assessments have been completed

Optional blood sample for retrospective pharmacogenetic exploratory analysis to be taken at Visit 2 or any subsequent visit after randomisation providing the patient has provided separate consent for the pharmacogenetics part of the study

Patients will complete a daily diary card recording date and time of dosing, fasting status, use of concomitant medication, oral body temperature twice daily and any changes in the medical state of the patient. A new diary card will be given to the patient at each clinic visit. The patient should bring their completed diary card to each of their clinic visits for review and discussion with clinical staff. Data on diary cards will not be entered into the eCRF directly but information will be reviewed with clinical staff to enable them to record date and time of dose on selected days in the eCRF and support accurate recording of compliance, concomitant medication and AEs in the medical records and eCRF.

Clinic staff will contact patients twice weekly via telephone in order to monitor any AEs, assess general health status, ensure that the patients are without fever and to ascertain whether an additional clinic visit is required.

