### 6.4.3 Recording of adverse events

#### Time period for collection of adverse events

Adverse Events will be collected from time of signature of informed consent and throughout the treatment period and the follow-up period (until Visit 7 or last study-related contact).

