## **8.4 Informed consent**

The Principal Investigator(s) at each centre will:

- Ensure each patient is given full and adequate oral and written information about the nature, purpose, possible risk and benefit of the study
- Ensure each patient is notified that they are free to discontinue from the study at any time
- Ensure that each patient is given the opportunity to ask questions and allowed time to consider the information provided
- Ensure each patient provides signed and dated informed consent before conducting any procedure specifically for the study
- Ensure the original, signed Informed Consent Form(s) is/are stored in the ISF
- Ensure a copy of the signed Informed Consent Form is given to the patient

- Ensure that any incentives for patients who participate in the study as well as any provisions for patients harmed as a consequence of study participation are described in the informed consent form that is approved by an Ethics Committee.

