### 13.3 Pregnancy

All outcomes of pregnancy should be reported to AstraZeneca.

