#### 13.3.1 Maternal exposure

Women of childbearing potential are not allowed to be included in this study (refer to Section 4.1). Should a pregnancy still occur, the investigational product should be discontinued immediately, the patient withdrawn from the study and the pregnancy reported to AstraZeneca.

Pregnancy itself is not regarded as an adverse event unless there is a suspicion that the investigational product under study may have interfered with the effectiveness of a contraceptive medication. Congenital abnormalities/birth defects and spontaneous miscarriages should be reported and handled as SAEs. Elective abortions without complications should not be handled as AEs. All initial reports and outcomes of pregnancies (spontaneous miscarriage, elective termination, ectopic pregnancy, normal birth or congenital abnormality) should be followed up and documented even if the patient was discontinued from the study.

If any pregnancy occurs in the course of the study, then investigators or other site personnel inform appropriate AstraZeneca representatives **within one day** ie, immediately but no later than the **end of the next business day** of when he or she becomes aware of it.

The designated AstraZeneca representative works with the investigator to ensure that all relevant information is provided to the AstraZeneca Patient Safety data entry site within 1 day for fatal and life threatening events or 5 days for all other SAEs, see Section 6.4.4, and within 30 days for all other pregnancies.

The same timelines apply when outcome information is available.

The pregnancy module in the eCRF is used to report the pregnancy together with a pregnancy fax report page which is sent to Patient Safety when a pregnancy is identified. The Pregnancy Outcome Report is used to report the outcome of the pregnancy. These reports should be sent through to the Data Entry Site within 30 calendar days of the Investigator becoming aware.

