#### 13.3.2 Paternal exposure

Male patients must refrain from fathering a child during the study and 3 months following the last dose (refer to Section 5.1).

Pregnancy of a patient's partner is not considered to be an adverse event. However, the outcome of any pregnancy occurring from the date of the first dose until 3 months after the last dose must be reported to AstraZeneca **within 5 days** and documented as specified in Section 13.3.1.

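### Male patients are asked to report a partner pregnancy only during the study, but the reporting duty runs to 3 months after the last dose

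*Protocol*

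**What the plan says.** Section 5.1, item 1, gives male patients three instructions. Abstaining from unprotected sex and from sperm donation, and the recommended double-barrier contraception, both run from dosing until 3 months after the last dose. The third sets a different period: "Male patients should inform the investigator if their partner becomes pregnant during the study".

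Section 13.3.2 sets the sponsor's reporting window: "the outcome of any pregnancy occurring from the date of the first dose until 3 months after the last dose must be reported to AstraZeneca". The limit is 5 days, and documentation follows Section 13.3.1. The same section also states: "Male patients must refrain from fathering a child during the study and 3 months following the last dose". Section 13.3 adds the general rule: "All outcomes of pregnancy should be reported to AstraZeneca".

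For a pregnancy already known, Section 13.3.1 says that initial reports and outcomes "should be followed up and documented even if the patient was discontinued from the study".

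**The concern.** A site can report only what it learns, and for a partner pregnancy the male patient is the natural source. The protocol tells him to speak up for a shorter time than the site is obliged to report. Someone who follows Section 5.1 to the letter has no reason to mention a pregnancy that begins after his last visit, even if it falls within the 3 months that Section 13.3.2 covers.

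What is at stake is first notification of possible exposure through the father. The protocol thought this important enough for a 3-month contraception rule and a 5-day reporting limit. If the patient information repeats the Section 5.1 wording, the Section 13.3.2 duty could go unmet for such a pregnancy without anyone departing from the instruction they were given.

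**Working it through.** There is no stated figure to reproduce. The check compares the two windows and then counts days.

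**What period the patient instruction covers**

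- Section 3.1 describes the diary as kept during the study and puts Visits 1 to 7 in brackets. It also gives the total duration of the study for a patient as 7 to 9 weeks.
- That duration is consistent with the schedule: 2 to 3 weeks of run-in + 4 weeks of treatment + 1 to 2 weeks to follow-up = 7 to 9 weeks. For the patient, the study therefore ends at Visit 7.
- Section 13.3.2 adds the 3 months after the last dose to the study period in its rule on fathering a child. The addition would not be needed if the study period already contained those months.
- Section 9.5 offers another reading, in which the study ends with the last visit of the last patient. It is carried through below.

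**Whether the heading of Section 5.1 explains the shorter wording**

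It does not. The rest of item 1 runs to 3 months after the last dose, and item 6 bans blood donation until 12 weeks after completion. The section goes beyond the study where its authors wanted it to.

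**Whether a planned contact closes the gap**

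- Section 6.4.3 collects adverse events until Visit 7 or the last study-related contact.
- Table 3 provides for telephone calls ("Clinic staff will contact patients twice weekly via telephone in order to monitor any AEs") but marks them only up to Visit 7.
- Section 13.3.1 governs follow-up once a pregnancy is known. It does not produce the first notification.

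**Length of the gap**

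Assumptions: 3 months = 91 days, and the last dose is on the day of Visit 6.

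Gap = 91 − (days from last dose to the end of the study for that patient).

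| Reading of when the study ends | Days after last dose | Gap |
|---|---|---|
| Patient's own Visit 7, text of Section 3.1 (1 to 2 weeks) | 7 to 14 | 91 − 14 = 77 to 91 − 7 = 84 days |
| Patient's own Visit 7, Table 3 | 3 to 18 | 91 − 18 = 73 to 91 − 3 = 88 days |
| Last patient's last visit, Section 9.5 | 3 to 91 or more | 0 to 91 − 3 = 88 days |

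In the last row, the gap is 0 for a patient whose last dose was at least 91 days before the last patient's last visit. It is 88 days for the last patient himself if his Visit 7 falls on day 3.

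On the per-patient reading, the uncovered part is 73/91 = 80% to 88/91 = 97% of the reporting window after the last dose. With the proposed wording the two windows coincide and the gap is 0.

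**The case against.** The strongest reply is that nothing here conflicts. Section 13.3.2 is the governing pregnancy section. It states the full window in mandatory terms, and Section 5.1 does not say that later pregnancies need not be reported. Both sentences can be followed. Section 13.3.2 also refers back to Section 5.1, where the other instructions to male patients give 3 months, so anyone briefing a patient from that item will mention the period. This stands as far as the investigator's rule goes: that rule is complete. It does not reach the patient, whose notification instruction is the one part of the item not carried to 3 months.

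A second reply is that any harm depends on the patient information. Section 8.4 requires the investigator to "Ensure each patient is given full and adequate oral and written information about the nature, purpose, possible risk and benefit of the study". The consent pages are not in the review copy, so whether patients are told the longer window cannot be judged. This also stands, and nothing is alleged to be missing there. If the patient information gives 3 months, only inconsistent wording remains.

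Third, the limit on adverse event collection does not govern, because Section 13.3.2 says a partner's pregnancy is not an adverse event. That is right. The limit is cited only to show when planned contact ends.

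Fourth, the day counts do not describe every male patient. Those who stop treatment early or withdraw from the study do not fit the assumption that the last dose falls at Visit 6. That is correct, and the ranges apply only under that assumption.

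**Conclusion.** The inconsistency is real and of low severity. Section 5.1 asks for notification over a shorter period than Section 13.3.2 requires for reporting. The shortfall per male patient is 77 to 84 days by the text or 73 to 88 days by Table 3. If the study is taken to last until the last patient's last visit, it is 0 to 88 days: early enrollees may be fully covered, late ones are not. These figures measure the gap in wording only. The number of missed notifications cannot be estimated from the protocol.

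No planned analysis is touched. Contraception is already required for the full 3 months, and few pregnancies are likely in about 60 patients, not all of them men, aged 40 to 80. Confidence is high that the two windows differ. Whether any report would be missed depends on patient information that could not be seen.

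**What to change.** In Section 5.1, item 1, replace *during the study* in the notification sentence with *from the first dose until 3 months after the last dose*. This matches Section 13.3.2 and the contraception rule in the same item. Remind male patients of the window at the existing Visit 7, and check that the patient information states the same period.

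The cost is one phrase, a verbal reminder and a document check. No extra visit, staff or sample is needed.

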## 5.2 Patient enrolment and randomisation

The Principal Investigator or delegate will:

1. Obtain signed informed consent from the potential patient before any study-specific procedures are performed.
2. Assign potential patient a unique enrolment number (E code), beginning with for example 'E0001001 (EXXXYYYY)' where XXXX reflects the centre number and YYY will be allocated sequentially to enrolled patients at each centre.
3. Determine patient eligibility. See Sections 4.1 and 4.2.
4. Assign eligible patients a unique randomisation code (patient number). Refer to Section 5.2.1.

If judged appropriate by the Investigator, a patient who initially fails screening may have a repeat enrolment. If a patient is re-enrolled they will be assigned a new E code.

If a patients withdraws from participation in the study, then his/her enrolment/randomisation code cannot be reused.

### 5.2.1 Procedures for randomisation

A dynamic randomisation approach will be applied. Randomisation codes will be generated by the Interactive Voice Response System (IVRS) / Interactive Web Response System (IWRS) provider using minimisation with biased coin assignment method which assigns

patients to treatments in a clinical trial with stratifying factors on which it is desired to achieve balance.

Patients will be assigned to treatment groups using IVRS / IWRS. Routines for this will be described in the IVRS/IWRS user manual that will be provided to each centre.

Randomisation codes will be assigned to patients who are eligible for randomisation. Randomisation will be stratified for use of inhaled corticosteroids. Patients will be randomly allocated to AZD5069 50 mg bd, AZD5069 80 mg bd or placebo in a 1:1:1 ratio.

Patients who are withdrawn after randomisation will not be replaced.

The randomisation code will be loaded into AstraZeneca Global Randomisation System (GRand).

### **5.3 Procedures for handling patients incorrectly enrolled, randomised or initiated on investigational product**

**Patients who fail to meet the inclusion/exclusion criteria** should not, under any circumstances, be enrolled or randomised. There can be no exceptions to this rule.

Where patients that do not meet the selection criteria are enrolled in error but are not yet randomised the procedures included in the protocol for the discontinuation from the study must be followed.

Where patients that do not meet the selection criteria are incorrectly randomised, incorrectly started on treatment, or where patients subsequently fail to meet the study criteria post-initiation, a discussion should occur between the AstraZeneca Study Delivery Team Physician and the Investigator regarding whether to continue or discontinue the patient from treatment. The AstraZeneca Study Delivery Team Physician is to ensure all such decisions are appropriately documented. In situations where an agreement cannot be reached, the patients should have their study therapy stopped and be discontinued from the study.

### **5.4 Blinding and procedures for unblinding the study**

#### **5.4.1 Methods for ensuring blinding**

This will be a double-blind study. AZD5069 will be provided as capsules for oral administration and with matching placebo capsules of the same size, weight and colour. Patients in all treatment arms will take the same number of capsules of investigational product or placebo ie, 4 capsules bd.

As the leucocyte count (including neutrophil data) will potentially be unblinding to site and study personnel, the data will be transferred from the local laboratory performing the analysis to the central laboratory. The results for Visit 1.1 will be communicated to the sites, but for all other visits (Visits 2-7) the central laboratory will review the data and notify the site if values are above the ULN or if a patient needs to be recalled for repeat sampling or needs to

be withdrawn from the study. Furthermore, to ensure that the investigator is not unblinded by only patients on active treatment being recalled, a number of patients with a normal leucocyte count will be randomly selected for repeat leucocyte assessments. Full details of the above process are detailed in the laboratory specifications.

Leucocyte (including neutrophil) count measurements performed by the central laboratory to investigate leucocyte stability will not be made available until the end of the study to ensure the study blind is not compromised. These data will also not be made available for blind review.

#### 5.4.2 Methods for unblinding the study

Individual treatment codes, indicating the treatment randomisation for each randomised patient, will be available to the investigator(s) or pharmacists from the IVRS/IWRS. Routines for this will be described in the IVRS/IWRS user manual that will be provided to each centre.

A copy of the randomisation scheme will also be made available to the PK bioanalyst, to enable the analysis of samples from patients who have received active treatment to be prioritised. This documentation will be placed in a secure location until the end of the study.

The treatment code should not be broken except in medical emergencies when the appropriate management of the patient requires knowledge of the treatment randomisation. The investigator documents and reports the action to AstraZeneca, without revealing the treatment given to the patient to the AstraZeneca staff.

AstraZeneca retains the right to break the code for SAEs that are unexpected and are suspected to be causally related to an investigational product and that potentially require expedited reporting to regulatory authorities. Treatment codes will not be broken for the planned analyses of data until all decisions on the evaluability of the data from each individual patient have been made and documented.

### 5.5 Treatments

#### 5.5.1 Identity of investigational product(s)

The investigational products used in the study are listed in the table below. The capsules will be packaged in blisters containing 64 capsules each, sufficient for 8 days' dosing.

**Table 4 Identity of Investigational Products.**

Investigational product	Dosage form and strength	Manufacturer
AZD5069	capsule 20 mg	AstraZeneca AB
AZD5069	capsule 50 mg	AstraZeneca AB
Placebo for AZD5069	capsule	AstraZeneca AB

## 5.5.2 Doses and treatment regimens

The investigational product will be taken orally twice daily, with doses approximately 12 hours apart (4 capsules in the morning and 4 capsules in the evening). The first dose of investigational product will be taken in the clinic at Visit 2. All other doses will be taken by the patient in accordance with their normal routine, unless the patient is taking part in the PK sub-study when the morning dose at Visits 4 and 6 should be taken in the clinic after pre-dose assessments. No food should be consumed within the 2 hours prior to the scheduled dose and for one hour after taking the dose.

In the event of an abnormal absolute neutrophil count (ANC) or leucocyte count (according to local laboratory measurements), patients should not take more than 4 doses of investigational product from the time of the abnormal blood test. Patients will be informed that they should not take the morning dose of investigational product 2 days after the first abnormal blood test without first obtaining consent from the clinic that it is appropriate to do so.

The patients will receive a box of medication containing 4 blister packs for the whole treatment period at Visit 2.

## 5.5.3 Additional study drug

No additional study drug is used in this study.

## 5.5.4 Labelling

Labels will be produced in accordance with Good Manufacturing Practice (GMP) and local regulatory guidelines. The labels will fulfil GMP Annex 13 requirements for labelling. Label text will be translated into local language.

## 5.5.5 Storage

All study drugs should be kept in a secure place under appropriate storage conditions. The investigational product label on the box specifies the appropriate storage.

## 5.6 Concomitant and post-study treatment(s)

### 5.6.1 Medication allowed during the study

Patients can continue with the following existing treatments during the study at a stable dose to be determined by the investigator:

- short acting  $\beta$ 2 agonist (SABA)
- short acting muscarinic antagonist (SAMA)
- long acting  $\beta$ 2 agonist (LABA), including ultra LABA
- long acting muscarinic antagonist (LAMA)

- inhaled corticosteroids (ICS)
- ICS/LABA combination.

Patients should refrain, if possible, from taking specified medication (as detailed in [Table 5](#)) prior to clinic visits where lung function assessments are performed.

Other drugs, including inhaled and oral respiratory medications, are permitted provided the dose is stable for at least 4 weeks prior to screening (Visit 1.1) and throughout the study.

Other medication, which is considered necessary for the patient's safety and well being, may be given at the discretion of the investigator and recorded in the appropriate sections of the eCRF.

### 5.6.2 Medication restrictions

Patients should refrain from taking restricted medications prior to clinic visits associated with lung function assessments (Visits 1.1, 2 and 3 to 7).

**Table 5** Restriction of medication during the study

Treatments to be restricted	Time limits prior to clinic visit (hours)
Short acting $\beta$ 2 agonist (SABA)	6
Short acting muscarinic antagonist (SAMA)	8
Long acting $\beta$ 2 agonist (LABA)	12
Ultra-LABA	12
Long acting muscarinic antagonist (LAMA)	12
Oral $\beta$ 2 agonists	6
Oral $\beta$ 2 agonists slow release formulations	24
Glucocorticosteroid (GCS)/LABA combination therapy	12
Ipratropium	6
Tiotropium	12

